5.1.3 Dose Modifications for Febrile Neutropenia

For participants already dosed reduced for reasons other than febrile neutropenia (e.g., neuropathy), dose reduction must start from the level at which the febrile neutropenia occurs.

Episode of Febrile Neutropenia	Action
First Episode of Febrile Neutropenia	Maintain current brentuximab vedotin dose with quinolone prophylaxis, or reduce one dose level (investigator's discretion).
Second Episode of Febrile Neutropenia	Quinolone prophylaxis and reduce one dose level.
Third Episode of Febrile Neutropenia	Quinolone prophylaxis and reduce one dose level.
Fourth Episode of Febrile Neutropenia	Quinolone prophylaxis and reduce one dose level.

 Table 5-B:
 Treatment Modification Guidelines for AVD-Brentuximab Vedotin for All Cycles

Dose Level	Brentuximab Vedotin	AVD
1	1.2 mg/kg	Full dose

-1	0.9 mg/kg	Full dose
-2	0.6 mg/kg	Full dose
-3	0	Full dose
-4	0	0.75

Quinolone prophylaxis: antibacterial therapy is required for all cycles after an initial episode of febrile neutropenia. Suggested regimen can be altered based on availability, allergies, or ANC trends (e.g., levofloxacin **750** mg PO daily, Days 6-13 and Days 20-27). Ciprofloxacin is not preferred due to being a moderate CYP3A4 inhibitor and caution should be exercised due to drug-drug interactions (See Appendix XIII).

Participants who are unable to receive at least 4 doses of brentuximab vedotin will not receive further therapy on study.

See Section 6.1 for a complete listing of potential adverse events and Section 6.1.1 for special precautions and safety issues.

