4.1.1 Definition of Dose-Limiting Toxicity (DLT)

During cycle 1, any AE resulting in a dose delay in AVD-BV therapy of \geq 7 days is considered a DLT, which requires discontinuation of protocol-specified therapy and withdrawal from the study. Please refer to Table 5-A in Section 5.1 for specific guidelines. In subsequent cycles, the brentuximab vedotin dose may be withheld or reduced according to the guidelines provided in Section 5.1. If two sequential doses of AVD+BV or AVD alone are held due to unresolved toxicity, leading to a treatment delay of an additional 2 weeks (i.e., 4 weeks between doses), protocol treatment will be discontinued. Please see Section 4.6.1 for criteria for permanent treatment discontinuation.

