4.6 Criteria for Permanent Removal from Treatment

After enrollment, participants will be permanently withdrawn from study treatment for any of the following reasons. In the event of withdrawal from treatment, the reason for study treatment removal and the date the participant was removed must be documented in the Off Protocol Treatment Form in AdvantageEDCSM. See Section 8.4 on evaluations to be performed at early discontinuation of therapy.

4.6.1 Participants who experience a delay of over 7 days in cycle 1 will be removed from protocol therapy. For subsequent cycles, if two sequential doses of AVD + BV or AVD alone are held due to unresolved toxicity, leading to a treatment delay of an
additional 2 weeks (i.e., 4 weeks between doses), the participant will be taken off protocol therapy. The participant will be followed for survival and may resume AVD treatment off study.

- 4.6.2 Severe toxicities as outlined in Section 5.0.
- 4.6.3 Progressive lymphoma at any time while on study.
- 4.6.4 Voluntary withdrawal.
- 4.6.5 The investigator has the right to remove participants from study for clinical reasons which he or she believes to be life threatening or resulting in significant morbidity to the participant.
- 4.6.6 Any participant who develops HBV reactivation or acute Hepatitis B as defined by the reappearance of a previously suppressed hepatitis B surface antigen, a positive IgM hepatitis B core antibody, and a positive viral load. Any participant with Hepatitis B or C who has worsening liver function as defined by Section 5.2.5 will also be removed from study.
- 4.6.7 Participants who become pregnant or breast-feed.
- 4.6.8 Participants with progressive disease at the end of cycle 2 will be removed from study treatment, while participants with stable disease may be removed from the study treatment at the discretion of the local responsible investigator. Progressive or stable disease defined at cycle 2 will be based by CT criteria only, as FDG-PET has yet to be validated in HIV-associated HL.
- 4.6.9 If found by central pathology review to not have the diagnosis of HIV-HL.

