5.0 DOSE MODIFICATIONS/TOXICITY MANAGEMENT

5.1 Brentuximab Vedotin Dose Modifications

Intrapatient Dose Reductions for Starting Dose of 1.2 mg/kg Every 2 Weeks.

No further dose reductions will be permitted beyond 0.6 mg/kg of brentuximab vedotin. Participants not tolerating a dose of 0.6mg/kg will continue with standard dose AVD at the discretion of the investigator.

Dose Level
1.2 mg/kg
0.9 mg/kg
0.6 mg/kg

Table 5-A: Treatment Modification Guidelines for Brentuximab Vedotin for All Cycles

Event	CTCAE v5.0	Action to be Taken	
	Grade		
Allergic reactions, or	Grade 1-2	For first reaction:	
Acute infusional		• Hold the infusion and wait 30 to 60 minutes	
reactions/ cytokine		(depending upon the reaction severity).	
release syndrome		 (depending upon the reaction severity). Treat reactions with diphenhydramine 1 mg/ (max 50 mg), or follow local instituti guidelines. Depending on the reaction severi dexamethasone 0.2mg/kg (max 10mg) IV show be used or follow local institution guidelines. Upon resolution of the symptoms, at a physician's discretion, it may be possible resume treatment by administering an H2 bloch approximately 30 minutes before restarting a infusion. Acetaminophen can also be considered Brentuximab vedotin may be administered at h of the previously administered rate at a discretion of the investigator. 	
		 For subsequent doses: Utilize diphenhydramine with or without acetaminophen as pre-treatment for all subsequent infusions. Dosing will be administered over the shortest infusion period that was well tolerated. If Grade 1-2 infusion reactions recur despite the above measures, either during re-challenge or subsequent treatments: 	

Event	CTCAE v5.0	Action to be Taken	
	Grade		
		 Take the measures outlined above. With subsequent dosing, add dexamethasone 0.2 mg/kg (max 10mg) IV or equivalent to medications above prior to infusion. 	

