	Grade 3	 Stop infusion immediately. Administer diphenhydramine hydrochloride 1 mg/kg IV (max 50 mg), dexamethasone 0.2mg/kg (max 10mg) IV (or equivalent), bronchodilators for bronchospasms, and other medications as medically indicated. Once symptoms recover, brentuximab vedotin should not be resumed for that course. Subsequent courses of brentuximab vedotin may be considered at physicians' discretion. All subsequent infusions will use the following premedications prior to infusion, diphenhydramine hydrochloride 1 mg/kg IV (max 50 mg), dexamethasone 0.2mg/kg (max 10mg) IV (or equivalent). In addition, the infusion will be administered at 50% of the previous infusion rate. 	
	Grade 4	 Stop infusion immediately. Administer diphenhydramine hydrochloride 1 mg/kg (max 50mg) IV, dexamethasone 0.2 mg/kg (max 10mg) IV (or equivalent), and other anaphylaxis medications as indicated. Epinephrine or bronchodilators at the discretion of the investigator will be administered as indicated. Hospital admission for observation may be indicated Discontinue brentuximab vedotin. 	
Anaphylaxis	Any grade	If anaphylaxis occurs, immediately and permanently discontinue administration of brentuximab vedotin and administer appropriate medical therapy.	
Pancreatitis	Grade 2	 Withhold dose until toxicity has returned to baseline, then continue on protocol therapy but resume at one dose reduction. If Grade 2 pancreatitis recurs after one dose reduction, the participant must be removed from protocol therapy. 	
	Grades 3-4	Permanently discontinue brentuximab vedotin.	
Peripheral	Grade 1	Continue at same dose level.	

Event	CTCAE v5.0	Action to be Taken	
	Grade		
Neuropathy	Grade 2	 Treatment is to be delayed until neuropathy improves to Grade 1 or baseline. Brentuximab vedotin will be reduced by one dose level for subsequent treatments once peripheral neuropathy returns to baseline or returns to a grade 1. Participants who experience a delay of over 7 days in cycle 1 will be removed from the study. For subsequent cycles, if two sequential doses of brentuximab vedotin are held due to unresolved toxicity, leading to a treatment delay of an additional 2 weeks (i.e., 4 weeks between doses), participants will have the option to discontinue protocol therapy or continue study with AVD with dose adjustments in vinblastine as clinically necessary based on the level of neuropathy on the day of treatment as per standard label/summary product characteristics. 	

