8.4 Early Discontinuation of Therapy

- 8.4.1 Participants discontinuing therapy early (i.e., PD or stable disease, administrative reasons, participant non-compliance, etc.) will have a medical history update and complete physical examination. The examination will include performance status and blood drawn for the following studies within 1 month after treatment discontinuation, unless otherwise noted. See Section 4.7 for a list of reasons for study termination. Participants will be followed for survival only for 5 years after the last date of treatment:
 - 8.4.1.1 CBC with differential.
 - 8.4.1.2 Serum chemistries: electrolytes (Na, K, Cl, bicarbonate, Ca, Mg, and phosphorus), glucose, blood urea nitrogen (BUN), creatinine, total bilirubin, alkaline phosphatase (ALP), LDH, total protein, albumin, AST and ALT.
 - 8.4.1.3 CD4 and CD8 cell count (do not repeat if done within 1 month from removal from treatment).
 - 8.4.1.4 HIV-1 RNA viral load to be assessed by any FDA-approved viral load assay (evaluated at the local laboratory, do not repeat if done within 1 month from removal from treatment).
 - 8.4.1.5 Pharmacokinetic/Immunogenicity studies in select Phase II participants only. See Section 10.1 and Appendix IX for time points and sample processing.
 - 8.4.1.6 Blood samples will be taken for analysis of latent and HIV reservoirs. See Section 10.0 and Appendix XII for time points needed, sample processing, and shipping instructions (do not repeat if done within 1 month from removal from treatment).
 - 8.4.1.7 Plasma samples to be taken for EBV tumor DNA studies. See Appendix XI for sample processing and shipping instructions. This will only be performed on the Phase II portion of the study.
 - 8.4.1.8 Plasma samples to be taken for and cytokine studies. See Appendix XI for sample processing and shipping instructions. This will only be performed on the Phase II portion of the study.

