	Grade 3-4	 Withhold dose until toxicity is ≤ Grade 2 or has returned to baseline, then continue on protocol therapy but resume at one dose reduction of brentuximab vedotin. If non-hematological Grade 3-4 toxicity recurs after one dose reduction, the patient must be removed from protocol therapy Patients who experience a delay of over 7 days in cycle 1 will be removed from the study. For subsequent cycles, if two sequential doses of brentuximab vedotin are held due to unresolved toxicity, leading to a treatment delay of an additional 2 weeks (i.e., 4 weeks between doses), the patients will be taken off protocol therapy, and brentuximab vedotin will be discontinued. Participants will have the option to be taken off protocol or continue study with just AVD without brentuximab vedotin.
Electrolyte Abnormalities	Grade 1-4	 Continue at same dose level, provided electrolyte toxicity is not medically consequential and has been readily corrected If electrolyte abnormality is medically consequential, refer to guidelines above for non-hematologic events

^a Patients who develop Grade 3 or 4 electrolyte laboratory abnormalities may continue study treatment without interruption but should receive appropriate medical therapy at the discretion of the investigator.

^b GCSF will be administered on Days 2-10 and 16-24 throughout each 28-day cycle using standard doses. Pegfilgrastim may be substituted for GCSF and administered on days 2 and 16.

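### Rules on continuing AVD after brentuximab vedotin is stopped or delayed contradict each other, and for participants without a documented response they decide whether progression is still followed

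*Combined protocol and SAP*

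**What the plan says.** **Who may continue AVD**

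- AMC protocol 5.1.3, repeated in French protocol 10.6.1.5: "Participants who are unable to receive at least 4 doses of brentuximab vedotin will not receive further therapy on study".
- AMC 5.1: "Participants not tolerating a dose of 0.6mg/kg will continue with standard dose AVD at the discretion of the investigator". In Table 5-B, level -3 sets brentuximab at zero with AVD at full dose.
- AMC Table 5-A, grade 2 neuropathy with two sequential brentuximab doses held: "participants will have the option to discontinue protocol therapy or continue study with AVD with dose adjustments in vinblastine". The grade 3 row offers the same choice.
- AMC 4.6.10: after recurrent grade 3 neuropathy AVD may continue, but this is worded for participants who have already had two cycles of the combination.
- Non-hematologic grade 3-4 row with two sequential brentuximab doses held, French protocol 10.6.1.2: "the patients will be taken off protocol therapy, and brentuximab vedotin will be discontinued". The next sentence reads: "Participants will have the option to be taken off protocol or continue study with just AVD without brentuximab vedotin". AMC Table 5-A carries the same pair.

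**Delay in cycle 1**

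- AMC 4.1.1 makes a delay of 7 days or more a DLT, "which requires discontinuation of protocol-specified therapy and withdrawal from the study".
- AMC 4.6.1: "Participants who experience a delay of over 7 days in cycle 1 will be removed from protocol therapy".
- AMC 4.2 lets treatment resume when the cycle 1 delay is under 7 days.

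**Follow-up after stopping**

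- AMC 4.5 and 8.3 follow those who stop after CR or PR for recurrence and survival, and those who stop for progression or other reasons for survival.
- AMC 8.4.1, on early discontinuation: "Participants will be followed for survival only for 5 years after the last date of treatment".
- AMC 4.6.1 says a participant removed for delay is followed for survival and may take AVD off study.

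**The concern.** These sentences decide two things at once: whether a participant whose brentuximab has been stopped still receives AVD as study treatment, and whether anyone goes on looking for progression. The primary phase II endpoint is 2-year PFS, and the French protocol (section 16.0) says French and US data are pooled for analysis. If two sites can read the same event differently, one may keep a participant on AVD with the cycle 2 and end-of-treatment scans and the six-monthly CTs. The other may move the same participant to survival-only contact. Deaths are captured either way, so the gap is non-fatal progression. The trigger is toxicity, so such censoring cannot be assumed unrelated to outcome. Section 11 gives no censoring rule for participants who leave therapy without progression.

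**Working it through.** **1. The non-hematologic row.** The first sentence takes the participant off protocol therapy; the second offers a choice between leaving and staying on study with AVD. Both can have effect only if protocol therapy means brentuximab alone. AMC 5.1.2 uses the term that way for pulmonary toxicity, but 4.6.1 uses it for the whole regimen.

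**2. The four-dose sentence.** Two doses per cycle make the fourth dose Cycle 2 Day 15. Two routes put a participant under opposing rules:

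- Doses at 1.2, 0.9 and 0.6 mg/kg on consecutive treatment days, then intolerance: 3 doses received. Section 5.1 allows AVD; 5.1.3 ends study therapy.
- Two doses in cycle 1, then grade 2 or 3 neuropathy with both cycle 2 doses held: 2 doses received. Table 5-A offers AVD; if brentuximab then stops for good, 5.1.3 ends study therapy.

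Only 4.6.10 carries a matching threshold (two cycles = 4 doses), and only for recurrent grade 3 neuropathy.

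**3. Cycle 1 delay.**

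| Delay | 4.2 (resume) | 4.6.1 (remove) | 4.1.1 (Phase I DLT) |
|---|---|---|---|
| Under 7 days | applies | no | no |
| Exactly 7 days | no | no | applies |
| Over 7 days | no | applies | applies |

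The consequence also varies. It is removal from therapy in AMC 4.6.1 and the AMC non-hematologic row. It is removal or withdrawal from the study in AMC 4.1.1, the AMC neuropathy and thrombocytopenia rows, and French 13.1.

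**4. Link to progression follow-up.** The first on-treatment restaging scan is on Days 22-28 of cycle 2, after dose 4. Anyone removed for a cycle 1 delay, or before dose 4, leaves before any scheduled scan could document CR or PR. That participant falls under the survival-only branch of 4.5 and 8.3, and the assessments listed in 8.4.1 contain no imaging. For someone who stops after a documented CR or PR, 4.5 and 8.3 keep recurrence follow-up, whereas 8.4.1 states no such exception and 4.6.1 mentions survival only.

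**5. Size, as illustration.** Inputs from section 11.2: 2-year PFS 85%, 95% interval of ±10 points, 51 participants.

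- Plan's figure: n = 1.96² × 0.85 × 0.15 / 0.10² = 48.98, so 49, within 2 of the stated 51.
- Half-width = 1.96 × √(0.85 × 0.15 / n). At n = 51: 9.8 points.
- The documents give no number affected. Assume 3 to 5 are censored early. At n = 48: 10.1 points; at n = 46: 10.3 points.
- Extreme bounds if those observed have 85% PFS and the others all fail or all succeed. For 3 unobserved: 0.85 × 48 / 51 = 80.0% to (0.85 × 48 + 3) / 51 = 85.9%. For 5: 0.85 × 46 / 51 = 76.7% to (0.85 × 46 + 5) / 51 = 86.5%.

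These bounds are not confidence limits.

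**The case against.** The strongest reply is that the wording is untidy but the endpoint is largely protected. Four parts of it deserve weight.

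- *Responders are kept.* A reader might infer that leaving protocol therapy always means survival-only follow-up. The documents do not support that: 4.5 and 8.3 retain recurrence follow-up after CR or PR, and the examples in 8.4.1 (progression, stable disease, administrative reasons, non-compliance) can be read as aimed at non-responders. This stands, and limits the problem mainly to those without a documented response. It does not remove the mismatch with 8.4.1 and 4.6.1.
- *The 7-day rule belongs to Phase I.* Section 4.1.1 sits under the Phase I heading, the MTD is already recorded, and section 11.2 allows Phase I data to be combined only if there were no DLTs. A reader might infer that 4.1.1 withdraws phase II participants at day 7; its placement does not support that. For phase II what remains is an uncovered day and an inconsistent consequence.
- *The sentences can be partly reconciled.* The four-dose rule could be a floor on every AVD permission, as 4.6.10 hints, and the non-hematologic row could mean brentuximab only. Neither reading is written down, and sites could differ.
- *Some variation is intended.* The protocol gives investigators or participants a choice in 4.6.10, 5.1 and the neuropathy rows. A different decision at two sites is not in itself a contradiction, and the repair should not force a single outcome on every event.

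**Conclusion.** The contradictions are in the current text of both protocols, except that 4.1.1 and 4.6.10's Phase I/II setting apply as set out above and the French protocol has no DLT section. They reach the primary endpoint for participants who leave without a documented CR or PR, because their status then decides whether non-fatal progression is looked for. For responders the follow-up sections conflict among themselves.

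The size is uncertain and the precision effect is small: 0.3 to 0.5 points of half-width under an assumed 3 to 5 of 51, just past the planned 10. A reader might attribute that loss wholly to the contradictions. The documents do not support this, since participants removed under a perfectly consistent rule would lose the same follow-up through the survival-only provision; the share due to contradiction alone cannot be estimated. The weightier issue is toxicity-related loss of progression data, whose direction and extent the documents do not allow one to quantify. The point should be fixed, but it does not undermine the sample size calculation.

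**What to change.** 1. Reconcile AMC 4.1.1, 4.2, 4.6.1, 4.6.10, 5.1, Table 5-A and 5.1.3, and French 10.1, 10.6.1 and 13.1, so that they no longer contradict each other. Use protocol therapy in one sense, cover a delay of exactly 7 days, and separate leaving treatment from leaving the study. Keep any discretion that is intended. Which treatment rule applies is for the clinical team; no view is offered here.
2. Reconcile AMC 4.5 and 8.3 with 4.6.1 and 8.4.1, and make the matching changes in the French follow-up sections (9.5, 9.6 and 13.1).
3. State that participants who stop brentuximab or all protocol therapy without progression remain on the existing schedule of progression assessments for PFS.

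The cost is a few amended sentences in each protocol and the already scheduled CTs for a few more participants.

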5.2 AVD-Brentuximab Vedotin Dose Modifications (applies to all cycles)

5.2.1 Hematologic Toxicity

Although it is common practice to attenuate doses or delay treatment due to cytopenias alone, recent studies have shown that in the non-HIV setting for cHL patients receiving delays results in suboptimal treatment outcomes^{77,78}. Participants will receive full doses of AVD on schedule on Days 1 and 15 of each 28-day cycle without treatment delays, unless neutropenic fever or documented infections are present.

5.2.2 Febrile Neutropenia

See Section 5.1.3 for AVD-brentuximab vedotin dose modification instructions for febrile neutropenia.

5.2.3 Transfusions

Erythrocyte and platelet transfusions will be administered as needed at the discretion of the treating physician.

5.2.4 Severe Infection

Severe infection (NCI CTC Version 5.0, Grade 3 or 4) due to chemotherapy-related neutropenia requires a decrease in the doses of vinblastine and doxorubicin to 75% of the last dose received for the next cycle. Re-escalation is at the discretion of the treating physician.

5.2.5 Impaired Hepatic Function

Table 5-C.

Please see Table 5-C below for the appropriate dose adjustments based on total bilirubin and AST. In cases of obstruction of the biliary duct by a tumor mass, a biliary drainage stent may be placed prior to chemotherapy. Values must be within protocol eligibility at treatment initiation.

Table 5-C:Total Bilirubin with Appropriate DoDose Adjustments		Doxorubicin and	d Vinblastii	ıe		
	Drug ¹	Total Bilirubin:	Total Bilirubin:	Total Bilirubin:	Total	

Drug ¹	Total Bilirubin:	Total Bilirubin:	Total Bilirubin:	Total
	< 1.5	1.5 – 3	3.1 – 3.5	Bilirubin:
	AST: < 60	AST: 60 - 180	AST: > 180	> 3.5
Doxorubicin	Administer	Administer	Administer	Safety Not
	100%	50%	25%	Established
Vinblastine	Administer	Administer	Administer	Safety Not
	100%	50%	25%	Established

If participants are receiving atazanavir, please use only the direct bilirubin as an indicator 1. for dose reduction of doxorubicin or vinblastine, following the dose reduction guidance identically as for total bilirubin

5.2.6 Neuropathy

Once brentuximab vedotin has been discontinued, participants experiencing Grade 3 vinblastine-neuropathy (e.g., obstipation, weakness) may continue the study receiving AVD with dose adjustments in vinblastine as clinically necessary, based on the level of neuropathy on the day of treatment. Participants experiencing Grade 4 vinblastine neuropathy will have this drug omitted from all future cycles of AVD.

5.2.7 If a participant's weight has changed more than 10% from baseline or the prior dose, the new BSA must be used on the next cycle. For a weight change of 10% or less, doses may be adjusted according to the BSA or remain the same in conjunction with institutional guidelines.

